Specialised home assistance has been evaluated in patients undergoing oral chemotherapy. The programme consisted in home visits, 24/7 phone availability, and a weekly phone call and it has shown that the experimental group experienced a lower incidence of toxicities than the control group, but also a lower number of accesses to the reference hospital or other health facilities and a reduction of the number of days of hospital stay (28). Though positive, the results of this trial also showed increased costs. For such reasons, there are data that a phone-only nurse follow-up might be an alternative to answer to the patients'need with lower costs and thus it might determine a toxicity reduction when compared with standard monitoring (32-35).

The studies on the management of oral therapies show how fundamental it is that the involved nurses are highly specialised in the disease and trained to take immediate therapeutic decisions, such as the variation or the interruption of the treatment, through the use of pre-established and agreed protocols, that were previously shared with medical professionals (34). An educational programme on oral therapies might have the final aim of limiting the dose reductions and inadequate treatment withdrawals.

Another field of interest is the management of "acute events" that might happen between therapy cycles. Waiting for the subsequent cycle might cause a lack of reporting of some serious side event.

The vast majority of trials based on electronic monitoring evaluate the toxicities during planned visits (36-40). Only a few studies also included home control between hospital visits (through an interim phone call) (41-42). Even if data are contrasting, some data show that, by intensifying the treatment of toxicities and symptoms, the application of supportive care guidelines, as well as the training of the patient, might lead to a statistically and clinically reduction of the toxicity severity (42).

A systematic literature review on 50 studies showed that there are three types of distance interventions: treatment and side effect monitoring, but also phone-based follow up (rather than hospital follow up), and psycho-educational phone interventions (43).

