There is a need for a precocious diagnosis of side effects in order to have better clinical management and a reduction of the intensity and duration of these events.

Better toxicity management can impact on the correct administration of cancer drugs (dose intensity).

It is still debated by the scientific community which is the best modality and evaluation tools to be used. In particular, the main questions are:

- Side effect reporting by physicians and/or patients;
- Role of nurses in the evaluation of side effects;
- The impact of the evaluation tools (frequency, executor) on the reduction of time spent with toxicity, their severity and the adherence to cancer treatment.

The recent Basch study (52) confirmed that patients that use patient-reported outcome (PRO-CTCAE) as an evaluation tool for toxicity rather than standard monitoring have a benefit in terms of overall survival. This evaluation has been conducted on a setting of metastatic patients on chemotherapy (50-52). There is then the need for randomized multicentric clinical trials in different therapeutic settings (chemotherapy, targeted therapies, immunotherapies) to evaluate the possible impact of a planned, continuative nurse monitoring of these patients.

Being proposed and sustained by the multidisciplinary NICSO (Italian Network of Supportive Care in Oncology) and having as a primary objective the improvement of toxicity management, based on the Italian law DM 17 December 2004, the study is a non-profit trial and it is a part of the health assistance in order to better the clinical practice.

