**Exploratory:**

Variation of the oncology treatment dosage (dose intensity).

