### **3.3 Study duration**

The study will last 24 months. Patients' accrual will have a duration of 18 months, from the beginning of the trial. The study period will be 4 months for the immunotherapy and targeted therapy groups and 6 months for the adjuvant chemotherapy group.

The study can be interrupted earlier in case of oncological treatment discontinuation because of disease progression, unacceptable toxicity, or withdrawal of consent by the patient, or patient's death. In case of temporary suspension of the oncological treatment, patients will continue to be monitored according to the group they are assigned. The study ends with the end of the monitoring period, that is with the last phone call to the last enrolled patient.

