- c) in case of toxicities that need an urgent intervention (less than 12 hours): facilitation of the contact with the referral physician or, if the contact is not possible, suggestion to access to the hospital through the centre-specific modalities (access

to the emergency room, access to the supportive care service, and so on);

d) in case of not deferrable urgencies: direct access to the emergency room through the emergency services (118).

At the end of every phone call, the Nurse Operative Center gives a synthetic report of the detection and sends an appropriate email to the reference physicians (identified at the moment of randomisation).

During the evaluation period, according to the PRO-CTCAE (validated in Italian) (53) (Attachment 1, 2, 3), in both groups, a questionnaire for the monitoring of toxicities will be administered to each patient.

This questionnaire, which takes into consideration the previous week, monitors the frequency (F), severity (S), and intensity (I) of each symptom. A question about the number of days spent with toxicity will be performed. The administration of the questionnaire will be made through a pre-registered phone call (without an operator), which is based on an electronic score coding. This phone call does not overlap with the monitoring phone call in the specific randomisation group.

For the patients' privacy, every date coming from the project will be dealt with according to the current laws.

In each group, at the baseline visit, then every month, the EORTC QLQ-C30 questionnaire (Attachment 4) will be administered.

In both groups, there will be a monitoring activity of the number of unplanned hospital accesses (emergency room or specialist visits). An evaluation of the number of hospital admissions and days of hospital stay (due to toxicities) will be performed.

Finally, the dose intensity of the oncological drugs throughout the period of treatment will be monitored (it will be considered as the ratio between the administered dose and the planned dose). This aspect is fundamental not only for the management of the oncological therapy but also for the adherence to the recommendations of supportive care.

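### Dose intensity is defined without a time term, so a full but delayed course of cycles scores 1.00; how an early stop scores is left open

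*Protocol*

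**What the plan says.** Section 2 of the protocol lists variation in oncology dosage, labelled dose intensity, as its only exploratory objective. Section 4 (Operative aspects) says that "the dose intensity of the oncological drugs throughout the period of treatment will be monitored" and then defines the quantity: "it will be considered as the ratio between the administered dose and the planned dose". No time unit appears. Nothing there or elsewhere says whether planned dose means the whole planned course, the dose planned within the study period, or the dose planned for the cycles started.

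Section 3.3 (Study duration) sets follow-up at 6 months for adjuvant chemotherapy and 4 months for the other two groups. It foresees both situations that matter here. On early stops: "The study can be interrupted earlier in case of oncological treatment discontinuation because of disease progression, unacceptable toxicity". On pauses: "In case of temporary suspension of the oncological treatment, patients will continue to be monitored according to the group they are assigned". Neither statement is tied to the dose-intensity calculation.

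Section 1 (Background) presents dose intensity as a sign that cancer drugs are being given correctly, and expects it to respond to better toxicity management. In a passage about education on oral therapies, it gives a possible aim of "limiting the dose reductions and inadequate treatment withdrawals".

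**The concern.** Dose intensity is an amount of drug per unit of time. A ratio of two total doses is a relative total dose. The two agree when treatment runs on schedule and part when cycles are delayed, and delay is one of the ordinary responses to toxicity. If nurse monitoring led to fewer or shorter delays while the cycles were all given in the end, this endpoint would not register the gain.

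A second, softer problem concerns permanent stops. Because planned dose has no stated reference period, the same patient can be scored in two very different ways, and the protocol does not say which applies.

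What is at stake is the meaning of one exploratory comparison.

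**Working it through.** The protocol states no figure for dose intensity, so there is nothing to reproduce. The check applies its rule to simple cases.

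**Inputs from the protocol**
- Administered dose over planned dose, no time term (section 4).
- Study period of 6 or 4 months; temporary suspension and early discontinuation both foreseen (section 3.3).

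**Assumed input (not in the protocol)**
- A course of 6 cycles of 3 weeks, 18 weeks in all, one dose unit per cycle. Actual weeks run to the end of the last cycle given.

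**Measures compared**
- (a) Protocol ratio, planned dose over the whole course: given / 6.
- (b) Protocol ratio, planned dose only to the stop: given / cycles started.
- (c) Simple time-based ratio: (given / actual weeks) / (6 / 18).
- (d) Time-based ratio using the longer of actual and planned weeks: (given / max(actual, 18)) / (6 / 18).

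| Case | (a) | (b) | (c) | (d) |
|---|---|---|---|---|
| All 6 cycles full and on time | 6/6 = 1.00 | 6/6 = 1.00 | 1.00 | 1.00 |
| All 6 full, given over 22 weeks | 6/6 = 1.00 | 6/6 = 1.00 | (6/22)/(6/18) = 0.82 | (6/22)/(6/18) = 0.82 |
| Stop after 2 full on-time cycles (6 weeks) | 2/6 = 0.33 | 2/2 = 1.00 | (2/6)/(6/18) = 1.00 | (2/18)/(6/18) = 0.33 |
| 20% reduction in every cycle | 4.8/6 = 0.80 | 4.8/6 = 0.80 | 0.80 | 0.80 |

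Three things follow.
1. The delayed course scores 1.00 under both readings of the protocol's rule.
2. The early stop scores 0.33 or 1.00 depending on the reading.
3. The dose reduction scores 0.80 throughout, so the rule does capture reductions.

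Column (c) also shows that adding time in the simplest way would not reveal an early stop; column (d) handles both.

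**Does the study period rescue the rule?** Not in this example. Six months is about 26 weeks, and 22 weeks fits inside it.

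**A second assumed course, 8 cycles of 21 days (168 days)**
- Two 14-day delays: protocol ratio 1.00, time-based 168/196 = 0.86.
- A 7-day delay at each of the 7 intervals: protocol ratio 1.00, time-based 168/217 = 0.77.
- Stop after 4 cycles: 4/8 = 0.50 or 4/4 = 1.00. Stop after 2: 2/8 = 0.25 or 2/2 = 1.00.

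These delayed courses run past 26 weeks (182 days). If only dose given inside the window counted, with dosing on day 1 of each cycle, cycle 8 would start on day 147 + 28 = 175 in the first delay case, and the score would stay 1.00. In the second it would start on day 147 + 49 = 196 and be lost, giving 7/8 = 0.875, still above 0.77. A window therefore catches delay only in part.

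**The case against.** The strongest reply has four parts.

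**Early stops.** A reader might infer that the protocol cuts planned dose off when treatment ends, so that stops for toxicity count as full dose intensity. The text does not say so. The words about the treatment period describe when dose intensity is monitored. The natural sense of planned dose is the dose planned for the patient, which gives 0.33 in the example. This stands: 1.00 is a permitted reading, not the stated rule.

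**The background.** A reader might also infer that the ratio misses what the intervention is meant to prevent, and so would tend to show no difference. The Background names dose reductions and withdrawals, in connection with education on oral therapies, and does not name delays. Reductions are captured, and withdrawals are captured under the whole-course reading. This stands too. The relevance of delays rests on the Background's broader link between dose intensity and correct administration, and on the suspensions foreseen in section 3.3.

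**Reach.** The targeted-therapy and immunotherapy groups are followed for a fixed 4 months. If planned dose is counted over that window, or by calendar day for continuous oral drugs, skipped days lower the ratio. This stands, and makes fixed-course adjuvant chemotherapy the clear case.

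**Level of detail.** The reference period for an exploratory endpoint is commonly left to an analysis plan, and the objective is worded as variation in dosage, which a dose ratio does measure. This is fair for the denominator. It does not answer the missing time term: the protocol states an explicit rule under the name dose intensity, and the rule does not measure it.

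**Conclusion.** The point holds for delays. As defined, the measure is a relative total dose, and a fixed cyclic course given in full but late scores 1.00. In the assumed courses a time-based measure gives 0.82 for the 18-week course and 0.77 to 0.86 for the 168-day course. These sizes depend on the assumed regimens, because the protocol gives no cycle numbers or delay rates.

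For early stops the finding is an ambiguity only: after 2 of 6 full cycles the score is 0.33 or 1.00, and the text settles neither. The documents do not support saying that toxicity stops are scored as full dose, nor that the endpoint is insensitive to treatment changes in general.

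The consequence is small. The endpoint is exploratory, and neither the primary endpoint nor the sample size depends on it.

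**What to change.** Replace the definition in section 4 with relative dose intensity:

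(administered dose / the longer of actual and planned weeks) divided by (planned dose / planned weeks).

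Take the planned course within the 4- or 6-month study period as the reference for every patient, including those who stop for toxicity. Say how suspensions enter actual weeks and how dose given after the study period is treated. Show stops for progression or death separately, since they do not reflect toxicity management.

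In the assumed examples this gives 18/22 = 0.82 for the delayed course and 0.33 for the stop after 2 of 6 cycles, and leaves a 20% reduction at 0.80. For treatment planned to continue through the whole 4 months, planned and actual weeks coincide and the formula becomes administered over planned dose within the window.

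The cost is a few sentences of definition and one extra display. The current ratio does not need administration dates, so the sponsor must confirm that the eCRF holds them. No treatment or clinical rule changes.

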## 5. STATISTICS

### 5.1 Sample size

The recent events related to the COVID19 pandemics have slowed down the accrual of the study. For this reason, a revision of the sample size has been necessary.

The revision only involves group B and C, since the accrual of group A was completed according to the original version of the protocol.

#### Group A

Considering the lack of data from the literature about the duration of side effects, especially grade 3 and 4, but estimating a prevalence of about 15%, considering a power of 0.9 and an alpha value of 0.05, it is then necessary to have 207 patients for each arm of the study to show a reduction from 15% to 5% of the proportion of days spent with a grade 3 or higher toxicity.

#### Groups B and C

Considering the same lack of data, but estimating a prevalence of about 25%, considering a power of 0.72 and an alpha value of 0.05, it is then necessary to have 50 patients per

arm per group to show a reduction from 25% to 5% of the proportion of days spent with a grade 3 or higher toxicity.

The entire sample size is then formed by 614 patients, to be found among the 63 involved centres.

## **5.2 Data management**

The investigator of each centre, together with the designated personnel, is in charge of the report of the required information through the specific electronic case report form (eCRF), that is provided by the Promotor. Data collected in the eCRF are anonymous and the patient will be identified only through a specific code. All the data are elaborated and analysed by the study scientific committee. All data are archived anonymously according to the guidelines for the treatment of personal data in clinical trials (Italian law approved on 24th July 2008, Official Gazette of 14th August 2008). Genetic data are treated according to the authorization 8/2013 (general authorization on the treatment of genetic data). The access to these data is protected by the investigator of each centre.

## **5.3 Data analysis**

Qualitative variables are synthesized in absolute frequencies and percentages; quantitative ones through mean and standard deviation, maximum and minimum, median and interquartile range. The evaluation of the statistical significance of the differences between two main groups (nurse monitoring vs standard monitoring) will be analyzed through the Student's t-test for dependent groups in case of quantitative parameters. The chi-square test will be used to evaluate the statistical significance of the differences in qualitative parameters. The comparisons among groups will be performed at the end of the study. The statistical significance of the variations in time of quantitative variables will be performed through the two-way analysis of variance (ANOVA). A secondary analysis will be performed, aiming at evaluating the statistical significance of the differences in all the other parameters between the two groups.

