**3.2 Patients'classification and randomisation**

Eligible patients are split up into three subgroups according to the oncological treatment

- Patients on adjuvant chemotherapy
- Patients treated with oral targeted therapy for the first time
- Patients treated with immunotherapy for the first time

Within each subgroup patients are randomised to receive:

- ✗ a periodical nurse monitoring phone call, that is planned and agreed with the patient, together with an information sheet with advice about prevention and treatment of toxicities (Experimental group)
- ✗ an information sheet with advice about prevention and treatment of toxicities (Standard group).

1:1 randomisation will be performed via computer using the randomly permuted blocks system.

All participants are to give their written informed consent.

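### Section 5.3 words one nurse-versus-standard comparison and does not tie it to the three treatment groups in which 3.2 randomises and 5.1 sizes the trial

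*Protocol*

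**What the plan says.** - **Randomisation (Protocol 3.2).** Patients are divided by oncological treatment into adjuvant chemotherapy, oral targeted therapy and immunotherapy. "Within each subgroup patients are randomised to receive" either nurse calls plus the information sheet or the sheet alone, 1:1.
- **Sample size, group A (Protocol 5.1).** Power 0.9 and alpha 0.05 lead to "207 patients for each arm of the study to show a reduction from 15% to 5% of the proportion of days spent" with grade 3 or higher toxicity.
- **Sample size, groups B and C (Protocol 5.1).** Power 0.72 and alpha 0.05 lead to 50 patients per "arm per group to show a reduction from 25% to 5% of the proportion of days" with such toxicity.
- **Revision and total (Protocol 5.1).** "The revision only involves group B and C, since the accrual of group A was completed". "The entire sample size is then formed by 614 patients".
- **Analysis (Protocol 5.3).** The test addresses "differences between two main groups (nurse monitoring vs standard monitoring"). A secondary analysis addresses "differences in all the other parameters between the two groups". In both places the groups are the two arms. Treatment subgroup, stratum and the letters A, B and C do not occur in 5.3. Its one other mention of groups fixes only that comparisons are made at the end of the study.
- **Observation period (Protocol 3.3).** "The study period will be 4 months for the immunotherapy and targeted therapy groups and 6 months for the adjuvant chemotherapy group".

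The letters A, B and C appear only in 5.1. Matching them to the three subgroups of 3.2 is an inference from their order.

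**The concern.** The design treats the three settings as three two-arm comparisons, each with its own rates, power and size. The analysis section describes one comparison of the arms. Someone who programs 5.3 as written could run a single unstratified test and still be following the text. Someone who reads it together with 5.1 would run three tests. The protocol does not decide between them, so the choice could be made after the data are known.

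The answer for each setting is what is at stake. Section 1 argues for randomised trials across chemotherapy, targeted therapy and immunotherapy. One overall result is weighted about two thirds towards group A. It could be significant because of A alone and be taken as benefit in the other two settings, or it could miss a benefit confined to B or C.

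Combining the groups also raises a question of scale. Section 2 states the primary objective as a count of days, while 5.1 uses the proportion of days. Within one group with a common period the two nearly agree. Across groups observed for 6 and 4 months they do not.

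**Working it through.** **Inputs.** From 5.1: A, 15% against 5%, power 0.90, 207 per arm; B and C, 25% against 5%, power 0.72, 50 per arm each; alpha 0.05. Sidedness is not stated; two-sided is inferred because it reproduces the plan's figures.

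**1. Reproduce the plan's sizes.** Two-proportion formula, with p̄ the mean of p1 and p2:

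n0 = [1.96·√(2p̄(1−p̄)) + z_power·√(p1(1−p1) + p2(1−p2))]² / (p1−p2)²

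Continuity correction: n = (n0/4)·[1 + √(1 + 4/(n0·|p1−p2|))]²

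- A: n0 = 187.05, n = 206.6, so 207 per arm.
- B and C: n0 = 40.47, n = 49.97, so 50 per arm.
- Total: 2 × 207 + 4 × 50 = 614.

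One-sided or uncorrected versions give other numbers (for A 153, 172 or 188; for B and C 31 or 41). So 614 is the sum of three separate binary two-arm calculations.

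**2. Size of one overall test at the same planned rates.**

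- Control rate: (207 × 0.15 + 100 × 0.25)/307 = 0.1826. Nurse rate: 0.05.
- Power 0.90: n0 = 120.8, n = 135.4, so 136 per arm. The plan has 207 + 50 + 50 = 307 per arm.
- Share of patients from A: 414/614 = 67%.

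**3. What the overall test would detect.** Continuity-corrected power at 307 per arm, control rate 18.3%. The binary simulation used 400,000 replicates.

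| Effect present in | Nurse rate overall | Power, formula | Power, simulated | Own test of a responding group, simulated |
|---|---|---|---|---|
| A, B and C (as planned) | 5.0% | 0.999 | 0.9995 | A 0.92; B and C 0.75 each |
| A only | 11.5% | 0.61 | 0.61 | A 0.92 |
| B only | 15.0% | 0.16 | 0.16 | B 0.75 |
| B and C only | 11.7% | 0.57 | 0.575 | B and C 0.75 each |

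Only the first row is a protocol assumption; the others are illustrations.

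**4. Count against proportion of days.** Taking 30 days per month, 5% of the period is 0.05 × 180 = 9 days in A and 0.05 × 120 = 6 days in B or C. The planned reductions are 0.10 × 180 = 18 days and 0.20 × 120 = 24 days. The proportion doubles from A to B or C, but the count rises by only a third.

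**5. Three tests at 0.05.** The groups are independent, so the chance of at least one false positive if no group has an effect is 1 − 0.95³ = 14.3%. Simulated with the conservative continuity-corrected test, it is between 9% and 10%.

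**6. Precision within groups at the planned rates (95% half-width).**

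- A: 1.96·√(0.15 × 0.85/207 + 0.05 × 0.95/207) = 0.057.
- B or C: 1.96·√(0.25 × 0.75/50 + 0.05 × 0.95/50) = 0.134.

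**The case against.** The strongest reply is that 5.3 is silent on the point and does not contradict 5.1. It names the contrast and the type of test, and does not say that all 614 patients enter one analysis. Its two groups may simply be the two arms inside each subgroup. Randomisation within subgroups, separate sizing and a revision confined to B and C all favour that reading. How a contrast is applied across strata is often left to the SAP, which is not shown here. This stands as far as intent goes: a reader might infer that a pooled primary test is planned, and the protocol does not support that. It does not settle the wording, because 5.3 does describe a comparison, and taken literally that comparison is not the one 5.1 powers.

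Three further points stand:

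- **Size of the loss.** The low overall powers arise only under the pooled reading and only if the effect is confined to some groups, which the protocol does not assume. At the planned effects the overall test loses nothing. All these figures are on 5.1's binary scale; 5.3 assigns quantitative outcomes to a t-test, and no standard deviation is given from which its power could be computed.
- **Per-group answers as the aim.** Sections 1 and 2 also state the aim and primary objective for patients as a whole, and the remark on different settings is background. A stratified overall test would also fit the randomisation.
- **Error rate.** Three within-group tests raise a multiplicity question that must be answered in the same edit.

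**Conclusion.** The point holds as a mismatch of wording that should be resolved. Sections 3.2 and 5.1 set up three comparisons; 5.3 words one and leaves the subgroups out. Read literally, it is an unstratified test for which 5.1 gives no power (136 per arm would do, against 307) and which mixes planned control rates of 15% and 25% and periods of 6 and 4 months. Confidence is medium, because the within-group reading is plausible.

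Two stronger conclusions should not be drawn. The overall arm comparison is not biased, since allocation is 1:1 within each subgroup. Nor is the trial shown to be underpowered: the stated 0.90 and 0.72 reproduce within groups, on the binary planning scale. The 0.61 (A only) and 0.16 (B only) show what one overall result could conceal and do not forecast what will happen. The conclusion rests on two inferences: that alpha is two-sided, and that A, B and C are the three subgroups of 3.2.

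**What to change.** In Protocol 5.3:

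1. State that the nurse-versus-standard comparison matching 5.1 is made within each of A, B and C, and that the arm difference and its 95% CI are reported for each.
2. State how alpha is treated. Either each group is a separate question with its own conclusion at 0.05, or an adjustment applies because success in any one group would count.
3. If an overall comparison is kept, stratify it by treatment group, base it on the proportion of days as in 5.1, and say that it is not evidence of benefit in any single group. Label an arm-by-group interaction test as descriptive: its power is about 0.32 (A against B and C together) or 0.25 (three groups) if only A responds.

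In 5.1, add that 0.90 and 0.72 come from a binary two-proportion calculation within each group, so that they are not read as the power of a test on patients' mean proportions of days.

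The cost is a few sentences and a little more analysis, with no new patients or data. The downside is that B and C will have wide intervals. Adjusting alpha, if that option is chosen, would lower the power within each group below the stated values.

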**Secondary:**

- ✓ Incidence and duration of grade 1-2 toxicities;
- ✓ Number of emergency room accesses and unplanned specialist visits;
- ✓ Number of hospital admissions and days spent in the hospital because of treatment -related toxicities
- ✓ Evaluation of quality of life.

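### The only between-arm test named for quantitative outcomes ignores the baseline QLQ-C30; it would be valid on independent arms but imprecise, and a baseline-adjusted model costs nothing

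*Protocol*

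**What the plan says.** Quality of life is a secondary objective in Section 2 ("Evaluation of quality of life"). Section 4 gives the schedule: "In each group, at the baseline visit, then every month, the EORTC QLQ-C30 questionnaire (Attachment 4) will be administered". It is therefore an outcome with a planned starting value for every patient in both arms.

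Section 5.3 assigns methods by type of variable and does not mention quality of life by name. It says that "differences between two main groups (nurse monitoring vs standard monitoring) will be analyzed through the" test it then specifies as "Student's t-test for dependent groups in case of quantitative parameters". It then adds: "The statistical significance of the variations in time of quantitative variables will be performed through the two-way analysis of variance (ANOVA"). A secondary analysis is aimed at "evaluating the statistical significance of the differences in all the other parameters between the two groups", without a further model. On timing it says only: "The comparisons among groups will be performed at the end of the study".

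The protocol names no covariate, change score or analysis of covariance, and gives no QLQ-C30 scale, month, effect size, SD or correlation.

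**The concern.** A QLQ-C30 score is a quantitative parameter, so the general rule in Section 5.3 covers it, and the method that rule states for the arm comparison is a t-test without covariates. A patient's score before treatment usually predicts the later score. A test that leaves it out keeps that predictable variation in the error term.

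What is at stake is precision, chiefly in groups B and C, which Section 5.1 sets at 50 patients per arm after slow accrual. A real difference in quality of life is easier to miss there, and the observed difference also reflects whatever gap the arms happened to have at the start.

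**Working it through.** **Inputs from the protocol.** Patients per arm: 207 in group A and 50 in each of groups B and C (Section 5.1). Allocation is 1:1 (Section 3.2). QLQ-C30 is taken at baseline and monthly (Section 4).

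**Assumptions.** The protocol gives no figures for quality of life. I take r, the correlation between baseline and follow-up score, as 0.3 to 0.7; equal SDs at both times; a true difference of 0.5 SD where power is shown; and two-sided alpha 0.05.

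**The plan's own figures.** The two-proportion formula with pooled variance, continuity correction and two-sided alpha 0.05 gives 207 per arm (15% vs 5%, power 0.90) and 50 per arm (25% vs 5%, power 0.72). The total is 2 × 207 + 4 × 50 = 614, as stated. These figures concern toxicity. Here they only fix the numbers of patients.

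**Variance of the arm difference at one follow-up month, relative to the unadjusted t-test (= 1).**
- Analysis of covariance: 1 − r².
- Change score: 2(1 − r).
- Ratio of the two: (1 − r²) / [2(1 − r)] = (1 + r)/2, which is below 1 for every r below 1.

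| r | ANCOVA variance | Change-score variance | Equivalent n per arm, 50 / 207 | Power, 50 per arm, 0.5 SD: ANCOVA |
|---|---|---|---|---|
| 0.3 | 0.91 | 1.40 | 55 / 228 | 0.74 |
| 0.4 | 0.84 | 1.20 | 60 / 246 | 0.77 |
| 0.5 | 0.75 | 1.00 | 67 / 276 | 0.82 |
| 0.6 | 0.64 | 0.80 | 78 / 323 | 0.87 |
| 0.7 | 0.51 | 0.60 | 98 / 406 | 0.93 |

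Equivalent n is n / (1 − r²). Power is from the noncentral t distribution with noncentrality 0.5 × √(50/2) / √(1 − r²). The unadjusted test has power 0.70. A change-score test at r = 0.4 has 0.62, which is worse than ignoring baseline, because 2(1 − r) exceeds 1 whenever r is below 0.5.

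**Difference detectable with 80% power** (normal approximation, (1.96 + 0.84) × √(2/n), times √(1 − r²) when adjusted). Groups B and C: 0.560 SD unadjusted, and 0.535 / 0.485 / 0.400 SD at r = 0.3 / 0.5 / 0.7. Group A: 0.275 SD, and 0.263 / 0.238 / 0.197 SD.

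**Chance imbalance.** The SE of the baseline gap is √(2/n): 0.20 SD with 50 per arm and 0.098 SD with 207. A gap above 0.3 SD on a given scale has probability 2[1 − Φ(0.3/0.20)] = 0.13 in group B or C, and 2[1 − Φ(0.3/0.098)] = 0.002 in group A. A gap g shifts the expected unadjusted difference by r × g. For g = 0.3 SD and r = 0.4 to 0.7 that is 0.12 to 0.21 SD.

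**Does the two-way ANOVA supply the adjustment?** Suppose its factors are arm and time, with baseline as one time level. With one follow-up, the interaction tests the difference in change between arms, so it is the change-score row above. The arm main effect averages in a visit at which no effect can yet exist, which dilutes the difference. Neither reading uses baseline as efficiently as a covariate does.

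**The case against.** The strongest reply has four parts.

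*The test is valid.* On independent randomised arms an unadjusted t-test is unbiased and keeps its type I error. This stands. A reader might infer that chance imbalance biases the comparison, or that a baseline gap carries over in full. Neither follows: the imbalance is already in the t-test's standard error, and the shift given an observed gap is r times that gap.

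*Baseline may be used after all.* A reader might infer that quality of life is definitely analysed without its baseline. The protocol does not support that. Section 5.3 does not name quality of life, and its two-way ANOVA could include the baseline visit. The text is unclear rather than explicit. The ANOVA is, however, assigned to variation over time, and its arm-by-time form amounts to a change score.

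*This belongs in an analysis plan.* A missing covariate for a secondary outcome would not by itself be a finding. Section 5.3 does not stay silent, though: it names a test for arm differences in quantitative parameters, and that test takes no covariate.

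*The size is shown where it is largest.* This is fair. In group A, power at 0.5 SD is already above 0.99 without adjustment. If Section 5.3 means the two arms pooled over treatment groups (207 + 50 + 50 = 307 per arm), the gain at that effect size is negligible. The separate sample sizes per group suggest separate analyses, but Section 5.3 does not say so.

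The same sentence also calls the groups dependent, although the randomised arms are independent. That is a distinct and plainer error. Correcting it would still leave a t-test without baseline.

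**Conclusion.** The point holds as a matter of efficiency and clarity. The one arm comparison that Section 5.3 specifies for quantitative parameters takes no baseline covariate, and the role of the baseline visit in the ANOVA is not stated. For r between 0.3 and 0.7, adjustment removes 9% to 49% of the variance of the arm difference, equal to 5 to 48 extra patients per arm in each of groups B and C. At 0.5 SD, power there goes from 0.70 to between 0.74 and 0.93. Group A gains the same proportion, but it matters only for smaller differences.

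Both r and the 0.5 SD effect are assumptions, so the range is the result and no single value in it can be fixed from the protocol. The figures are for one follow-up month per patient. The conclusion does not touch the primary toxicity endpoint.

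**What to change.** In Section 5.3, state that QLQ-C30 is compared between arms within each treatment group by a model with arm and the same patient's baseline score as covariate. This can be analysis of covariance at one named month, or a repeated-measures model of the monthly post-baseline scores. Name the scale or scales and the month or contrast of interest, and report the adjusted difference with its 95% CI. If the two-way ANOVA is kept, state its factors and whether the baseline visit is one of its time levels. Correct the description of the arms as dependent in the same edit.

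The cost is a sentence or two of text. The baseline questionnaire is already scheduled, so no visits, patients or data items are added.
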